1. HYPOTHESIS

Pathologic complete response (pCR) is associated with improved survival and lower risk for distant metastases. Neoadjuvant Endo-HDR will increase pCR rates compared to concurrent chemoradiation (RT + Capecitabine). We expect similar locoregional control, decreased treatment time (1 week as opposed to 6 weeks), improved sphincter preservation rates, and lower acute and chronic toxicity.

2. ELIGIBILITY

Patients with low rectal cancer who are candidates for endorectal brachytherapy (non-obstructing lesions which can be adequately treated with this technique will be eligible for the study). Distal rectal tumors at 14 cm or less from the anal verge or rectosigmoid junction are included. Patients with T4 and/or presumed pathologic iliac/inguinal lymphadenopathy on PET/CT or MRI (>1.5 cm in diameter or necrotic appearing) are excluded.

3. BACKGROUND

3.1 Rationale

Locally advanced rectal carcinoma continues to be a major oncologic problem in the United States with approximately 40,000 new cases diagnosed in 2012. For stage II/III rectal carcinoma, adjuvant chemoradiation (1-3) and total mesorectal excision (TME) (4, 5) represent the major treatment advances that have increased cure rates over the past 30 years.

In the setting of TME, a landmark phase III German trial of stage II/III rectal cancer patients established neoadjuvant 5FU-based chemoradiation (NCRT) as standard of care over the same regimen given post-operatively (6). The preoperative arm showed superior local control (6% vs. 13% p=0.006), a complete pathologic response of 8%, a higher rate of sphincter preservation and less grade 3 toxicity compared to post-operative treatment. However, disease-free and overall survival (76% versus 74%, respectively) were no different because of the high rate of distant metastasis occurring in over 1/3 of patients (5yr DM 36 vs 38%, p=0.84). Importantly, those attaining a pathologic complete response had a decreased rate of distant metastasis and improved disease-free survival. Drawbacks to the regimen include acute grade 3 or 4 toxicity in 27% of patients, low compliance rates with postoperative chemotherapy (27 – 50%), and an overall decline in anorectal function shown by long-term studies (6).

Given the excellent locoregional control reported in TME surgical series, several trials have investigated whether certain patients may be spared preoperative radiotherapy (7-9). Two large randomized trials by Dutch and British investigators showed that a short preoperative course of hypofractionated EBRT (25 Gy in 5 fractions) followed by TME surgery decreased locoregional recurrence by 2/3 as compared to patients treated with TME surgery alone. In the Dutch trial, patients with mid and distal rectal cancers were most likely to benefit from radiotherapy. In these patients, preoperative radiation was shown to decrease locoregional recurrence by 5-fold (10% to 2%); however, the

hypofractionated preoperative EBRT regimen was associated with a significant increase in acute and chronic morbidity. Indeed, the Dutch study revealed that irradiated patients, when compared to surgery alone, had more perineal wound healing problems after abdominoperineal resection (29% vs. 19%), worsening deterioration of anal sphincter dysfunction, and more severe long-term effects related to sexual functioning both in males ($p=0.004$) and females ($p<0.002$) (10-12). Additionally, colleagues have reported a consistent negative impact on bowel function in those patients undergoing sphincter preservation (13). In reviewing the long-term data of the Swedish short course preoperative EBRT rectal cancer trial, Birgisson also reported a higher incidence of secondary tumors (9.5%) in patients treated with preoperative radiation when compared to patients having surgery alone (4.3%) (14).

Modern approaches to address the risk of distant metastasis and poor compliance with adjuvant systemic chemotherapy (following NCRT) have incorporated newer effective chemotherapy agents earlier in the treatment protocol. For example, oxaliplatin has been one of the most widely studied agents as a result of its proven efficacy when combined with 5-fluorouracil and leucovorin (FOLFOX) both in the metastatic and adjuvant settings for colon cancer(15). Initial phase II studies with the addition of oxaliplatin to standard 5-FU based NCRT appeared to show improved pathologic complete response rates compared to standard NCRT. However, two phase III trials clearly show that the addition of oxaliplatin during 5FU-based NCRT does not significantly improve pathologic complete response, locoregional control, distant metastasis or survival but does increase acute grade 3-4 toxicity by two to three-fold (16, 17).

One approach to limit toxicity from external beam radiotherapy is the use of intensity modulated radiation therapy (IMRT). IMRT can limit radiation dose to normal rectum (above and below the tumor) and surrounding organs at risk (OARs) such as bladder and sexual organs. IMRT utilizes multiple beams of radiation to treat the rectal tumor plus a margin and limits dose to OARs. While IMRT decreases radiation dose to normal structures, it requires an additional 2-3 cm margin for microscopic extension (clinical treatment volume=CTV), set-up error, and rectal motion (planning treatment volume=PTV). Furthermore, IMRT still requires 5-6 weeks of radiation with concurrent chemotherapy, is substantially more expensive than conformal radiation, and is especially prohibitive in countries where access to technology necessary for IMRT is limited (20). Based on the preliminary results of RTOG 0822 and others, it still remains to be determined whether IMRT confers a statistically significant improvement in pCR, toxicity rates and QOL relative to standard NCRT.

A novel approach to limit radiation toxicity is the use of high dose rate endorectal brachytherapy (Endo-HDR) (21). Endo-HDR involves the placement of a silicon multicatheter applicator within the rectum to deliver large doses to the rectal tumor and mesorectum with rapid dose fall off to the surrounding organs. An Iridium 192 high dose rate brachytherapy source attached to a wire is inserted into each catheter to deliver a high dose of radiation therapy the tumor. High dose rate brachytherapy has been well established in various malignancies (prostate, uterine, sarcoma, head and neck) to escalate radiation dose to the tumor over a short period of time while sparing normal

tissue. Compared with NCRT and IMRT, Endo-HDR delivers treatment internally to the tumor without having to pass through surrounding normal tissue and organs. It requires smaller margins (CTV/PTV=~1 cm) on the tumor since the applicator is positioned under fiducial guidance over the tumor without need for a margin for organ motion allowing greater sparing of OARs (22). Furthermore, the area of the rectum exposed to high dose radiotherapy is surgically removed at the time of resection which further minimizes chronic toxicity. Important structures that may be spared include bone marrow, small bowel, bladder, the autonomic nerves, sexual organs, anal sphincter and skin. Considering that 1/3 of patients will develop metastases, limiting bone marrow toxicity may contribute to better compliance with systemic treatment and allow for a better treatment strategy to target systemic recurrence. Another distinct advantage of Endo-HDR is the shortened treatment time (1 versus 6 weeks). Endo-HDR therefore provides a major logistic advantage for patients who may benefit from neoadjuvant therapy but who are geographically distant from radiation centers, elderly, or medically infirmed.

At the McGill University Health Center (MUHC), Vuong reported a phase II trial using high dose rate brachytherapy without concurrent chemotherapy to treat 285 (260 T3 tumors, 7 T4 tumors, and 18 T2 tumors and 38% were N+) rectal cancer within 10 cm from the anal verge from 1998-2007. The median age was 69 years (range 42-90) (23). Patients received four fractions of 6.5 Gy (26 Gy total) HDR-BT treatments in one week followed by a 6-8 week period of downstaging prior to resection. Treatment planning was CT-based with MRI, ultrasound imaging and use of fiducial markers using radioopaque clips placed under direct endoscopic visualization with the tumor bed defined as any visible disease seen in at the primary site or mesorectal nodal deposits. Patients with node positive disease at the time of surgery received adjuvant chemotherapy and EBRT. At a median follow-up time of 54 months, the 5 year actuarial local recurrence rate is 5%, with a doubling of pathologic complete response compared to standard chemoradiation (27%), < 1% grade 3-4 acute toxicity and no apparent increased long-term toxicity when compared to patients treated with TME alone. The disease-free survival is 65%, and the overall survival rate is 68% (23). Those patients attaining a pathologic complete response had improved survival and fewer distant metastasis. Grade 1-2 proctitis was noted in all patients starting 7-10 days after therapy and continuing until resection. While one patient experienced grade 3 toxicity, none had grade 4 proctitis. Surgical complications were limited to an anastomotic leak rate of 10% and a perineal wound infection rate of 12% comparable to standard surgical experiences alone. Importantly, Endo-HDR did not compromise the pelvic bone marrow function and was not associated with hematologic toxicity. Based on these promising results, a current NCI Canada trial randomizes rectal cancer patients treated with Endo-HDR followed by TME to either pre- vs. post-operative FOLFOX.

Although these are promising results supporting the use of Endo-HDR, a theoretical concern of using this treatment strategy to treat only the primary site and adjacent mesorectal nodes is the potential for increased pelvic nodal recurrence without elective treatment with external beam radiotherapy (24). Standard NCRT covers the internal iliac, perirectal lymph nodes, mesorectum, and primary tumor (25). Current radiation portals are derived largely from Gunderson and Sosin's detailed study of the pattern of

recurrence after bluntly dissected rectal cancers. However, modern surgical series in patients treated without external beam radiation have shown that the majority of pelvic failures occur locally in the anastomosis and presacral tumor bed and that the incidence of extramesorectal pelvic nodal failure is low both in overall incidence as well as an isolated source of failure (4, 26-28). Wiig, reporting on 100 cases of local recurrence after TME, concluded that all recurrences were within reach of the examining finger and at the tumor bed (26). In the same series, there was only one case of nodal recurrence in the lateral pelvic wall. In the Dutch TME referenced above, the rate of extramesorectal pelvic nodal failure was 1.6% in the TME alone arm versus 1.3% who received preoperative radiation therapy. Moreover, preoperative treatment of extramesorectal nodes with chemoradiation may not improve outcomes. In the MERCURY study, MRI-based assessment of tumor regression and circumferential margin were prognostic for survival after neoadjuvant chemoradiation (29). Importantly, the presence of MRI detected extramesorectal lymphadenopathy did negatively impact disease-free survival; however, the use of neoadjuvant treatment did not alter the negative outcomes of iliac node positivity (29).

3.2 Correlative Studies

3.2.1 FDG-PET

The motivation for HDR brachytherapy in the treatment of rectal cancer is that a localized high dose rate gradient will improve pathologic complete response rates when compared to the homogeneous dose delivery of IMRT. While the high dose rate aspect will enable a much higher biological effectiveness to the targeted region, it is important to note that according to the linear-quadratic model, normal organs are more sensitive to the effects of high dose rate than tumors. This makes the localization of the dose delivery an issue of concern.

In this situation, FDG-PET will be a valuable tool to monitor treatment effect on the primary tumor as it is believed to better correlate with tumor response than CT-based criteria (30). We will exploit this hypothesis by examining the relation between dose and response as measured by ¹⁸F-FDG uptake in ¹⁹²Ir HDR brachytherapy of rectal cancer at the voxel level as well as for the whole tumor. This strategy exploits another emerging concept that a single mean absorbed dose value is rarely indicative of tumor response.

The following sequence of events will take place (the first four are patient procedures and the last is a theoretical exercise): 1) an initial ¹⁸F-FDG PET/CT scan (Figure 1a); 2) 4 treatments of HDR ¹⁹²Ir brachytherapy designed to deliver a minimum of 26 Gy total to every voxel of the defined tumor region (Figure 1b); 3) a second ¹⁸F-FDG PET scan 8 weeks after treatment (Figure 1c); 4) resection of the tumor; 5) a comparison of pathologic tumor response with radiation dose distributions.

Consequently, the correlations we will be examining will be twofold: 1) the entire tumor and 2) the individual voxels. The whole tumor mean dose will be compared to the change in ¹⁸F-FDG uptake in the tumor region both in absolute and in relative

change. A similar approach holds for the voxelized data; however, voxelized data represents a challenge in dosimetry: the uncertainty inherent in the individual voxel absorbed dose outweighs its value. However, when large number of voxels are considered, such as those that constitute an entire organ or a binned ensemble, significant results can be obtained. This is often exploited in the form of dose volume histograms (DVHs). We will use both DVHs and binned results in our analyses.

3.2.2 DNA Damage Response

The effect of radiation on tumor cells is to cause irreversible injury to essential components of the cell. A commonly affected pathway is the DNA damage response pathway. We wish to compare how Endo-HDR versus NCRT affects this pathway. To do this, we will examine well-described genetic alterations (VEGF/EGFR, p53, BRAF, KRAS, PIK3CA, γ -H2AX, and XRCC1). We will determine whether particular mutations predict for pCR rates status post treatment. We will also correlate our findings with overall and disease-free survival.

3.2.3 Cancer Genome Sequencing to Determine Genetic Predictors of Response to Endo-HDR and IMRT

Whole cancer exome analysis will be performed on a subset of cases of strong responders and non-responders in an unbiased manner. Twenty thousand genes will be interrogated using tumor samples and whole blood using the Agilent capture platform and the Illumina HiSeq2000. Samples will be sequenced at a depth of 100-200X and analysis of these results will take into account clinical response. Correlation with clinical and pathologic response to therapy, disease free survival and overall survival will be performed against all the somatic genetic alterations found in each subset (32).

3.2.5 The role of infectious and inflammatory processes in colon carcinogenesis

The role of infectious and inflammatory processes in colon carcinogenesis is of intense interest since the colon is colonized with $\sim 10^{12-13}$ commensal bacteria with the potential to induce inflammatory processes if colonic epithelial homeostasis is disrupted. The importance of inflammation in CRC is demonstrated by the dramatic increase in incidence among individuals with Inflammatory Bowel Disease (IBD). Bacterial initiators and promoters of immunologically driven CRC have long been proposed. Supportive human epidemiologic data show that migrating populations adopt the cancer risk of the region to which they relocate. Over time, the investigative focus has been on either mutagen production by colonic bacteria or their conversion of dietary procarcinogens into DNA-damaging molecules. Despite considerable effort, no direct links between the metabolic activities of bacteria and sporadic CRC are established. To date, the strongest, yet limited, evidence suggesting that commensal microbiota contribute to CRC pathogenesis derive from select, usually immune, gene knockout murine models in which the incidence of colon tumors usually decreases under germ-free conditions. The idea that the microbiome structure confers disease potential is supported by data, for example, indicating that murine colitis or disease phenotypes are transmissible through the microbiome. In 2011, we initiated a project at Johns Hopkins in which primary, untreated CRC tumors along with flanking normal colon tissue from surgical specimens was

collected for microbial analysis. Microbial analysis included structural microbiology, classic anaerobic microbiology and deep sequencing of the tumor or normal tissue (mucosal)-associated microbiota. This project has yielded, to date a critical observations. In right CRCs examined to date, a marked biofilm is associated with the tumors and is also present on at least 40% of flanking normal tissues from the same patients. In contrast, no biofilms are detected on any left CRC tumors or on flanking normal colon tissues. These data suggest the microbial associations of right vs. left-sided CRC are distinct. Sequencing analyses have revealed trends to differences in specific microbial associations in right and left CRC. Left sided CRC analyzed to date have been from the descending and rectosigmoid region because most rectal cancer at JHH is treated before surgery with radiation and chemotherapy, both of which may modulate the microbiome, we have little information on microbial associations of rectal cancer. In conjunction with the endorectal brachytherapy trial for treatment of rectal cancer, we will collect 2 additional biopsies (tumor and normal) during the pre-treatment endoscopy (standard of care in current protocol). Biopsies are currently being collected for other correlative studies during this endoscopy and additional biopsies will not be taken if it interferes with patient care. Tissue will be snap frozen and used for microbial sequencing. Results will be analyzed in conjunction with ongoing CRC microbial studies (evaluations of right and left colon cancer) underway at JHH as well as correlative studies (tumor genetics) being conducted as part of the endorectal brachytherapy trial.

3.3 Preliminary Data

In order to accurately quantify the effects of a) dose rate and b) heterogeneity in the normal organs and tumors and consequently the relative merits and potential of HDR brachytherapy as an adjunct for rectal cancer treatment, we will use dose volume histograms (DVHs) for all sensitive normal organs as well as the tumors and compare the DVHs to the DVHs from the IMRT treatment plans (performed on patient diagnostic scans). In order to compare dose values from different modalities, brachytherapy and IMRT external beam therapy, a conversion based on radiobiological modeling and the linear-quadratic equation is used. The different voxel doses are converted to the biological effective dose (BED) (41, 42) and from there to equivalent 180-cGy fractions (43) used in the IMRT plan.

The formula for the biological equivalent dose (BED) is: $BED = D \left(1 + \frac{D/N}{\alpha/\beta} \right)$

where D is the total absorbed dose, N is the number of fractions (4 for the HDR brachytherapy; 28 for the IMRT plan) and *alpha* and *beta* are the radiobiological parameters for the linear-quadratic model of cell kill.

The process of conversion to 180-cGy equivalent dose takes into account the higher dose rate in HDR. Accurate, detailed absorbed dose calculations are useful only to the extent that they are biologically relevant and easily interpretable. The uniformity (or lack thereof) of absorbed dose distributions and their biological implications has been examined intensively, primarily in animal studies (44-46). The equivalent uniform dose

(EUD) model converts the spatially varying absorbed dose distribution into an equivalent uniform absorbed dose value that would yield a biological response similar to the one expected from the original dose distribution. This provides a single value that may be used to compare different dose distributions (43, 47, 48) and may correlate to single tumor response values rather than the mean absorbed dose. This EUD value is another example of how voxelized data may be grouped to provide more biologically relevant information at a larger scale.

[figure not shown]

Figure 1a.

Figure 1b.

Figure 1c.

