7.3 Intensity Modulated Radiation Therapy and Capecitabine

7.3.1 IMRT Planning

External radiotherapy will be based on contouring guidelines from the RTOG atlas and Radiation Therapy Oncology Group (RTOG 0822) with modifications described below.

Patients will undergo CT (required) and MRI simulation (optional) in the supine position with concurrent administration of IV and oral contrast. (IV contrast may be omitted for patients with contrast allergy or another contraindication.) The bladder should be full. A custom immobilization device such as a vac-loc bag or alpha cradle should be used to ensure consistent setup. An anal BB marker should also be placed at the time of simulation.

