7.3.1.2 Clinical Treat. Vol. (CTV) & Planning Treat. Vol. (PTV) for IMRT

The RTOG Anorectal Contouring Guidelines will be used to guide treatment planning for patients in the IMRT arm of this study (50). Two PTVs will be created according to these guidelines. PTV-Initial will consist of CTVA plus margin,

including pelvic lymph nodes, the mesorectum, and the primary tumor plus margin and will receive 45 Gy in 25 1.8-Gy fractions. PTV-Conedown will include the rectal primary tumor plus margin and will receive 5.4 Gy in 3 1.8-Gy fractions. The RTOG contouring guidelines for creating target volumes are summarized below.

PTV-Initial

CTVA consists of the following areas that must always be treated in rectal cancer and will be uniformly expanded by 0.5 cm to create PTV-Initial. This volume will receive 45 Gy (1.8 Gy x 25).

- Superior border: The recommended superior extent of the peri-rectal component of CTVA was at whichever is more cephalad: the rectosigmoid junction or 2 cm proximal to the superior extent of macroscopic disease in the rectum/peri-rectal nodes. This defines how much of the distal large bowel should be within CTVA. The most cephalad extent of CTVA will be higher than the peri-rectal component, in order to properly cover the internal iliac and pre-sacral regions. The most cephalad aspect of CTVA should be where the common iliac vessels bifurcate into external/internal iliacs (approximate boney landmark: sacral promontory).
- Inferior border: Minimum 2 cm caudal to gross disease including coverage of entire mesorectum to the pelvic floor. Unless radiographic evidence of extension to ischiorectal fossa, CTVA need not extend through the levator muscles. For very advanced anal or rectal cancers, extending through the mesorectum or the levators, the group's recommendation is to add ~1-2 cm margin up to bone wherever the cancer extends beyond the usual compartments. An MRI and/or PET/CT scan is strongly recommended in such cases.

CTVA will also include the following structures:

- Iliac Lymphatic CTV= Internal iliac vessels + 1.0 cm symmetrical expansion.
- Presacral Lymphatic CTV = 8mm anterior to anterior border of sacral bone (extending from S1-S5)
- Mesorectal and perirectal lymphatic CTV
- Posterior border: anterior border of the sacrum and gluteus maximus
- Lateral border: Ileum, piriformis and obturator muscles
- Anterior border should overlap 1cm into the bladder, vagina or prostate.

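### Section 3.3 converts a two-phase IMRT dose with a single N of 28, which can only understate IMRT biological dose: about 1.8 Gy for a 45-Gy voxel with no cone-down dose, at an assumed alpha/beta of 3

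*Combined protocol and SAP*

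**What the plan says.** Section 3.3 (Preliminary Data) states, in the future tense, that DVHs of the tumor and the sensitive normal organs under Endo-HDR will be compared with "DVHs from the IMRT treatment plans (performed on patient diagnostic scans"). To put both modalities on one scale: "The different voxel doses are converted to the biological effective dose (BED) (41, 42) and from there to equivalent 180-cGy fractions (43"). The BED formula is D(1 + (D/N)/(alpha/beta)), "where D is the total absorbed dose" and "N is the number of fractions (4 for the HDR brachytherapy; 28 for the IMRT plan"). No alpha/beta value is given, and nothing is said about handling phases separately.

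Section 7.3.1.2 describes the IMRT plan as two sequential phases. The elective volume "will receive 45 Gy in 25 1.8-Gy fractions". After that, "PTV-Conedown will include the rectal primary tumor plus margin and will receive 5.4 Gy in 3 1.8-Gy fractions". The cone-down target is the primary GTV, any involved nodal GTV and the presacral CTV, with a 0.5 cm margin. Section 7.3.4 confirms 28 fractions of 1.8 Gy in total.

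**The concern.** D/N stands for the dose per fraction. Dividing a voxel's total dose by 28 gives its true fraction size only if the voxel received that same dose on all 28 days. Tissue inside PTV-Initial but away from the cone-down volume receives most or all of its dose in 25 fractions, so D/28 is too small, and so is the BED.

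A simple identity exposes this: 45 Gy delivered in 1.8-Gy fractions must still be 45 Gy when expressed in 1.8-Gy fractions, whatever alpha/beta is. The rule as written does not return 45 Gy.

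At stake is the accuracy of the organ-sparing comparison that 3.3 sets out to make. The error falls on the IMRT side only and always in the same direction, so it does not average out over voxels or patients.

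**Working it through.** **Inputs**
- BED formula, and N = 28 for IMRT: section 3.3.
- Phase 1: n1 = 25 fractions, 45 Gy. Phase 2: n2 = 3 fractions, 5.4 Gy. Section 7.3.1.2.
- alpha/beta: not given. Assumed to be 3 Gy for normal tissue, with 2, 5 and 10 shown as a range.
- Assumed: the comparison IMRT plans follow the two-phase prescription of 7.3.1.2, as N = 28 implies.

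**The plan's own figure.** 45/1.8 + 5.4/1.8 = 25 + 3 = 28. A voxel receiving the full 50.4 Gy has D/N = 50.4/28 = 1.8 Gy and converts to exactly 50.4 Gy at any alpha/beta. The stated N is therefore right for the course as a whole.

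**Conversion.** Equating BEDs, the 1.8-Gy equivalent is BED / (1 + 1.8/(alpha/beta)).

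**Voxel with 45 Gy from phase 1 and no cone-down dose.** The rule uses 45/28 = 1.61 Gy per fraction; the true value is 45/25 = 1.8 Gy. At alpha/beta 3:
- True BED = 45 × (1 + 1.8/3) = 72.0; equivalent = 72.0/1.6 = 45.0 Gy.
- Rule BED = 45 × (1 + 1.607/3) = 69.1; equivalent = 69.1/1.6 = 43.2 Gy.

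| alpha/beta (assumed) | True BED | BED with N=28 | Change | 1.8-Gy equivalent with N=28 (true 45.0) |
|---|---|---|---|---|
| 2 | 85.5 | 81.2 | -5.1% | 42.7 |
| 3 | 72.0 | 69.1 | -4.0% | 43.2 |
| 5 | 61.2 | 59.5 | -2.8% | 43.7 |
| 10 | 53.1 | 52.2 | -1.6% | 44.3 |

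**General form.** Let a voxel receive d1 per fraction in phase 1 and d2 in phase 2, so D = 25·d1 + 3·d2. The two-phase BED exceeds the single-N BED by (25·d1² + 3·d2² − D²/28)/(alpha/beta), and the numerator simplifies to (25 × 3/28)(d1 − d2)². The shortfall in 1.8-Gy equivalents is therefore

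(75/28)(d1 − d2)² / (alpha/beta + 1.8).

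This is never negative, and it is zero exactly when d1 = d2, at whatever dose level.

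**Size in less extreme voxels, alpha/beta 3 (denominator 4.8)**
- 45 Gy in phase 1, no cone-down dose: 2.679 × 1.80²/4.8 = 1.81 Gy.
- 45 Gy in phase 1, 25% of the cone-down fraction dose (d2 = 0.45): 2.679 × 1.35²/4.8 = 1.02 Gy.
- 45 Gy in phase 1, 50% (d2 = 0.90): 2.679 × 0.90²/4.8 = 0.45 Gy.
- 40 Gy in phase 1, no spill (d1 = 1.6): 2.679 × 1.60²/4.8 = 1.43 Gy.
- 20 Gy in phase 1, no spill (d1 = 0.8): 2.679 × 0.80²/4.8 = 0.36 Gy.

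**The case against.** The best defence is that this is a simplification with little effect, and much of that stands.

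- The number 28 is not miscounted, and the formula is exact for any voxel with equal dose per fraction in both phases, not only inside the cone-down volume.
- The 45-Gy voxel with no spill is an extreme. Section 7.3.1.3.1 allows at most 40% of the bladder and of the femoral heads above 40 Gy, so most of each lies where the shortfall is at most about 1.4 Gy at alpha/beta 3, and less with spill.
- The missing alpha/beta matters far more. The Endo-HDR prescription of 26 Gy in 4 fractions converts to 26 × (1 + 6.5/3)/1.6 = 51.5 Gy at alpha/beta 3, but to 26 × (1 + 6.5/10)/1.18 = 36.4 Gy at 10.
- The method is attributed to cited references that I have not seen, and a page close to this text was missing from the copy I read. Phase-wise handling described there cannot be excluded.

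None of this makes the rule as written correct: it still fails the 45-Gy identity at every alpha/beta.

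A reader might also infer that the comparison is invalid because its IMRT plans are made on diagnostic scans, while 7.3.1 says "Patients will undergo CT (required) and MRI simulation (optional) in the supine position". The documents do not support that. Section 3.3 never claims to use the plans delivered to control patients, and a virtual IMRT plan for the same patient is a legitimate design. Substituting control-arm plans would compare different patients, some of whom may receive 3-D conformal treatment under 7.3.3. For the same reason, the understated quantity is the dose of the comparison IMRT plan, not the dose of the control arm.

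**Conclusion.** The point holds and is minor. With one N of 28, section 3.3 understates IMRT biological dose wherever a voxel's dose per fraction differs between the two phases, and never overstates it. The direction needs no assumption about alpha/beta. The size does: between 0.7 Gy (alpha/beta 10) and 2.3 Gy (alpha/beta 2) for a 45-Gy voxel without cone-down dose, falling quickly with spill or lower dose, and zero where the two phases deliver equal fractions.

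Two stronger readings should be resisted. A reader might infer that the error flatters Endo-HDR. It does the opposite: a lower IMRT organ dose makes Endo-HDR sparing look smaller. A reader might also infer that it weakens the trial's results. The BED-based DVH comparison is not an endpoint, power input or planned analysis in section 14, and the IMRT constraints in 7.3.1.3.1 are in physical dose, so neither the pCR analysis nor any patient's plan is affected.

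**What to change.** In section 3.3, replace the single IMRT value of N with a phase-wise rule: compute BED for each voxel from each phase's own dose grid (N = 25 for PTV-Initial, N = 3 for PTV-Conedown), add the two, and only then convert to 1.8-Gy equivalents. In the same place, list the alpha/beta used for each tissue, since without it the conversion is undefined for both modalities. If the phases are already summed this way in practice, it is enough to say so.

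The cost is a sentence or two in the protocol, dose exported separately by phase, and slightly more analysis. Section 7.1 provides for central review of plans but does not say that phase-level dose grids are kept, so the export would have to be requested explicitly. No prescription, constraint or clinical rule changes.
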